1. BACKGROUND AND RATIONALE

1.1. Background

Food allergy is a potentially life threatening condition that affects up to 8% of young children and 3 to 5% of the entire US population ([Gupta 2018](#)). Similar to many other childhood allergies, milk allergy sometimes persists into adulthood and, along with tree nuts and peanuts, is one of the most common foods that may cause anaphylaxis ([Fiocchi 2015](#), [Lifschitz 2015](#)). The current remedies for food allergy are food avoidance and treatment with medications such as injectable epinephrine for accidental exposures associated with severe allergic symptoms. Although recent progress has been made in the treatment of food allergy through allergen-specific oral immunotherapy (OIT), there is an unmet need for a new therapy in food allergy. The aim of OIT is to induce desensitization and increase the threshold for milk ingestion, and reduce the risks of allergic reactions after accidental ingestion; however, many subjects in OIT trials experience dose-related side effects that can hinder their compliance and the overall efficacy of OIT ([Vázquez-Ortiz 2013](#), [Martorell Calatayud 2014](#), [Mori 2017](#), [De Schryver 2019](#)). While it is known that allergic response to food is an IgE-mediated event, recent data suggest that the role of interleukin-4 (IL-4) and IL-13 may also play a significant role in food allergy pathogenesis ([Noval Rivas 2016](#), [Rial 2019](#)). This clinical study proposes to examine the effect of dupilumab, a monoclonal antibody, which blocks the action of these cytokines, to enhance the safety, tolerability and efficacy of milk protein OIT in subjects with significant allergy to milk.

The immune system in the gut actively induces an immune tolerant state to the proteins that are normally consumed. Food allergy occurs when the body has a break in this tolerance, which results in an abnormal immune reaction to food. Milk allergy is an IgE-mediated hypersensitivity reaction following the ingestion of normally innocuous milk protein. Cross-linking of milk-specific IgE (sIgE) bound to high affinity IgE receptors on mast cells and basophils triggers immediate degranulation, and the subsequent release of a diverse array of inflammatory mediators results in severe allergic symptoms such as hives, wheezing, vomiting and, in severe cases, anaphylactic shock. Release of these mediators also initiates type 2 helper T-cell (Th2) cytokine release, which results in eosinophil infiltration and creates a vicious cycle of chronic allergic inflammation. Like other forms of allergy immunotherapy, OIT to milk involves a slow up-dosing of exposure to allergen over time to desensitize or increase the threshold of reactivity to milk. Once reaching a target level of milk protein, subjects are continued on a maintenance dose of milk protein to maintain desensitization. Although many subjects on a maintenance dose of milk protein have demonstrated desensitization to milk (i.e. the ability to tolerate a level of exposure to milk without an allergic reaction), up to 95% subjects exhibit related adverse events (AEs) during OIT with 40% experiencing gastrointestinal (GI) symptoms ([Vázquez-Ortiz 2013](#), [Martorell Calatayud 2014](#), [Mori 2017](#), [De Schryver 2019](#)). While the majority of these are mild and decline with prolonged treatment, approximately 25% of patients experience more severe, unpredictable reactions. Roughly 20 to 30% of patients are unable to complete their up-dosing regimen due to side effects, of which the majority are related to the GI system. In those who do successfully desensitize, an additional issue with current OIT arises, specifically its limited ability to induce clinical tolerance (i.e. the persistence of desensitization after subjects are taken off of OIT) ([Keet 2012](#), [Suárez-Fariñas 2019](#)). In many of the studies with milk OIT, despite years of

immunotherapy, subjects lose their tolerance within weeks of halting daily milk intake, with only 50% or fewer patients maintaining a sustained unresponsiveness after 2 months off OIT.

Dupilumab, a fully human monoclonal antibody directed against interleukin-4 receptor alpha (IL-4R α), blocks the activity of IL-4 and IL-13 at both the type 1 and 2 receptor (Regeneron Pharmaceuticals, Inc. 2019, Sastre 2018). These receptors are present on a majority of the cell types involved in the induction and perpetuation of a Type 2 response, including B cells, eosinophils, macrophages, and basophils, and the binding of IL-4 and/or IL-13 has been shown to initiate a signal cascade that plays a critical role in modulating the expression of genes involved in both IgE class switching and Th2 cell differentiation. This pathway has been implicated in multiple atopic diseases via its ability to induce B Cell isotype class switching to allergen-specific IgE, Th2 cell proliferation, and proinflammatory cytokine production. Inhibiting both IL-4 and IL-13 signaling with dupilumab has demonstrated clinical efficacy in moderate-to-severe atopic dermatitis (AD), persistent, uncontrolled asthma, nasal polyposis, and is currently being investigated in eosinophilic esophagitis (EoE). It is known that oral allergen up-dosing during OIT induces up-regulation of IL-4 and IL-13 as well as other Type 2 inflammatory cytokines and pathway activity, which contribute to dose-limiting side effects of OIT such as GI (nausea, vomiting, diarrhea and abdominal pain), respiratory (wheezing and shortness of breath), and skin (generalized rash, pruritus, and angioedema) symptoms. By inhibiting the activation of IL-4R α , it is hypothesized that dupilumab may disable a number of signaling pathways involved in the development and progression of allergic responses.

This study will explore whether dupilumab has the ability to enhance immunomodulatory effects of OIT by decreasing Type 2 responses, decreasing production of milk-specific IgE, and potentially increasing the milk-specific IgG4 response, which will result in improved safety and tolerability of OIT up-dosing as well as improved efficacy as determined by the ability to tolerate a higher cumulative dose of milk protein during a double-blind, placebo-controlled food challenge (DBPCFC) after 18 and 24 weeks of therapy compared to placebo. In addition, the study will evaluate whether dupilumab influences known biomarkers important in the allergic response such as a reduction in allergen-specific immunoglobulin sub-class switching to IgE, decrease in basophil activation, and decreased Th2 cytokine levels.

Additional background information on the study drug and development program can be found in the Investigator's Brochure.

This protocol has been designed to explore whether dupilumab can decrease the number and/or severity of abdominal-related events, especially eosinophil activation associated with EoE.

1.2. Rationale

1.2.1. Rationale for Investigational Study

This study will investigate whether addition of dupilumab, a fully human monoclonal antibody directed against IL-4R α , will improve OIT in subjects with milk allergy. This study will seek to demonstrate that addition of dupilumab to milk protein OIT will enhance the safety, tolerability, and efficacy of OIT. This will be determined by assessing whether treatment with dupilumab provides an enhanced ability to tolerate a higher cumulative dose

of milk protein during a food challenge after 18 weeks of treatment compared to placebo when given concomitantly with milk protein OIT and whether treatment with dupilumab allows for more rapid up-dosing of milk during desensitization. The differences in safety and tolerability will be assessed through an evaluation of treatment differences in AEs and study drop-out rates.

OIT has demonstrated efficacy in desensitizing food allergic subjects through the promotion of physiologic changes that result in the suppression of an allergic response to the ingested food antigen (Pajno 2018). Desensitization is defined as the ability to tolerate a higher threshold of food allergen without an allergic reaction, while consuming the food regularly. Successful desensitization has been demonstrated in the majority of patients undergoing milk OIT, with rates of success varying depending on the specific definition of desensitization (i.e. milligrams of protein tolerated) and OIT protocol used.

The first randomized, controlled trial of milk OIT, which including treatment with egg, suggested significantly higher rates of desensitization in those receiving OIT compared to a control group (64% vs. 35%, respectively) (Staden 2007). In the first randomized, placebo-controlled study of milk OIT, patients receiving OIT saw an increase in median OFC threshold from 40 mg to 5140 mg after 13 weeks of treatment with 500 mg milk protein, with 36% of those receiving OIT maintaining their tolerance two months after treatment cessation (Skripak 2008). The milk protein dose was escalated to a median of 7000 mg in an open-label follow-up, resulting in 46% of patients tolerating an OFC of 16,000 mg (Narisety 2009). Recent work by Mori et al. mirrored these positive results, with 73% of children in their cohort reaching complete or partial desensitization (Mori 2017).

Additional research has demonstrated significantly greater rates of desensitization in those receiving 1 to 2 g daily milk OIT following sublingual immunotherapy (SLIT) compared to SLIT alone (70% vs 10%; p=0.002); however, results also indicated the effects of milk OIT may have limited durability, with 40% of patients (intent-to-treat) regaining reactivity after several months of milk avoidance (Keet 2012). Long-term follow-up of both the Keet and Skripak studies additionally highlight the potential limitation in durability, with less than one-third of patients fully tolerating milk 3 to 5 years after the completion of OIT (Keet 2013). Furthermore, despite favorable rates of desensitization, a majority of patients still experience significant AEs, primarily GI-related, during the course of OIT, as outlined in Section 1., with approximately 20-30% unable to complete their up-dosing regimen.

Studies have demonstrated the successful use of omalizumab, a monoclonal anti-IgE antibody, in significantly increasing the threshold of reactivity in milk- and multi-food-allergic patients when used as an adjunct during milk- and multi-food OIT (Wood 2016, Andorf 2018). Through its binding of free serum IgE, omalizumab is hypothesized to decrease mast cell and basophil surface-bound IgE and, thus, decrease degranulation and allergic response following allergen exposure. While results indicate a significant reduction of AEs during OIT in those receiving omalizumab compared to placebo, patients receiving adjunct omalizumab continued to experience OIT-related AEs, the majority of which were GI in nature. Additionally, results have indicated a lack of efficacy in the ability of omalizumab to increase long-term tolerance after OIT is discontinued. Each of these issues highlights the unmet need

for a safer and more reliable adjunct to OIT treatment that enables rapid and long-lasting protection. Dupilumab as an adjunct to daily OIT may meet this need given its additional inhibition of a number of signaling pathways involved in the development and progression of allergic responses beyond its suppression of allergen-specific IgE production.

1.2.2. Rationale for Study Design

Milk protein OIT, with and without dupilumab, will be tested in a 2-arm, double-blind, randomized, parallel-group, study in subjects with confirmed milk allergy. Pediatric subjects will be enrolled as children represent the majority of subjects with milk allergy and are a greater risk for accidental ingestion of milk. Dupilumab/placebo treatment for 16 weeks as an adjunct to 14 weeks of daily oral milk treatment will be evaluated, followed by maintenance period of 6 weeks of daily oral milk treatment with concomitant dupilumab or placebo. Two treatment groups are required to provide informative controls and minimize bias on clinical endpoints: dupilumab plus milk protein OIT and placebo plus milk protein OIT. Subjects will be treated for 16 weeks with either bi-weekly SC dupilumab or placebo. After the first 4 weeks, subjects will begin a 14 week up-dosing regimen of daily oral milk protein OIT. The study will assess an up-dosing regimen up to a maximum of 1000 mg over the following 14 weeks of the study. Subjects who achieve 1,000 mg daily dose of milk protein by week 18 will maintain this dose, as tolerated, following the week 18 DBPCFCs. Subjects not achieving 1000 mg by week 18 will continue to updose to the target maintenance dose of 1000 mg after the week 18 DBPCFCs until the week 24 DBPCFCs.

This design allows for a direct comparison between adjunct dupilumab plus OIT to placebo plus OIT during the 18-week double-blind treatment period. It will also evaluate the effect of increasing milk protein OIT, defined as an increase in the proportion of subjects who pass a DBPCFC.

1.2.3. Rationale for Dose Selection

1.2.3.1. Dose and Regimen for Dupilumab

A SC dose of 300 mg Q2W was recently approved in the US for treatment of moderate-to-severe AD in adults. Doses of 300 mg Q2W and 300 mg QW were shown to have an acceptable safety profile in adult AD patients in 3 phase 3 studies. In addition, 300 mg Q2W had an acceptable safety profile in a phase 2b study in adults with persistent asthma ([Wenzel 2016](#)). Dosing regimens based on age and weight have recently been approved in the US for the treatment of moderate-to-severe AD in those aged 6 to 17 years.

The doses selected for this study are the approved dosing regimens used in the treatment of AD in individuals aged 6 years and older per the full prescribing information (FPI) for Dupixent® (revised 06/2020). Additional dose regimens selected for use in those aged 4 to 5 years are consistent with data derived from previous studies of the treatment of AD and asthma in those under the age of 12 years.

In study R668-AD-1412, children aged 6-17 years received doses up to 4mg/kg QW for 4 doses, where exposures similar to those in adults receiving 300 mg Q2W were achieved. Significant improvements in measures of AD were noted in these children, with an

acceptable safety profile. As with many monoclonal antibodies, weight is the most significant covariate affecting dupilumab pharmacokinetics. The weight-based doses chosen for treatment in this study are chosen such that patients should achieve similar dupilumab exposure in serum to that observed at the Food and Drug Administration (FDA)-approved adult dose for moderate-severe atopic dermatitis (300mg Q2W), based on pharmacokinetic modeling of the data from study R668-AD-1412.

Refer to Section 6.1.1.2. Dosage, Preparation, and Administration for complete description of dupilumab and placebo for dupilumab for this study. Dupilumab will be administered SC in-clinic by trained clinical staff at least 30 minutes prior to the ingestion of the in-clinic milk OIT dose in order to allow for an accurate attribution of AE relatedness to study drug or milk. The administration of the loading dose of dupilumab will allow systemic concentrations to reach steady-state faster. Rapid attainment of target saturating concentrations may yield a rapid clinical response within 4-week period of dupilumab pre-treatment by suppressing Type 2 effector cell function, which is believed to be responsible for the allergic GI side effects of OIT. Dupilumab blockade of IL-4/IL-13 in AD, an immune-driven disease, reduced skin lesions and suppressed at 4 weeks the mRNA expression of genes related to T-cells, dendritic cells, eosinophils, inflammatory pathways, and Th2-inducing chemokines, whereas increases or insignificant decreases were observed with placebo. The correlation between these mechanistic changes and rapid improvement in clinical measures of disease activity, including Eczema Area and Severity Index (EASI) and Scoring Atopic Dermatitis (SCORAD) scores, support a milk protein OIT study design with only 4 weeks of dupilumab SC pre-treatment ([Hamilton 2014](#)). Rapid improvements in forced expiratory volume in 1 second (FEV1) and fractional exhaled nitric oxide have also been observed within 4 weeks in dupilumab studies in asthma ([Wenzel 2013](#), [Wenzel 2016](#)). The results in other indications suggest 4 weeks of dupilumab treatment significantly suppresses Type 2-mediated responses.

1.2.3.2. Dose and Regimen for Milk Oral Immunotherapy

Concurrent with blinded dupilumab dosing, subjects will begin milk protein OIT beginning at week 4 with an initial daily dose of 10 mg milk protein, escalating to a maximum of 1000 mg protein per day (see **Table 1**). This 1000 mg maintenance dosing regimen has previously been shown to provide significant clinical efficacy and consistent kinetics of the sIgG4 and sIgE response ([Keet 2012](#)). The milk protein OIT regimen target of 1000 mg per day may be clinically effective for desensitization for accidental milk exposure (about 1 oz).

2. STUDY HYPOTHESIS/OBJECTIVES

2.1. Hypothesis

We hypothesize that treatment with the IL-4 receptor alpha-chain-targeting antibody, dupilumab, will increase the likelihood of desensitization over the course of 18 weeks and decrease the rate and severity of adverse events associated with cow's milk OIT.

2.2. Primary Objective

To assess whether dupilumab as adjunct to milk oral immunotherapy (OIT) compared to placebo improves desensitization and safety, defined as an increase in the proportion of subjects who pass a double-blind placebo-controlled food challenge (DBPCFC) to at least 2040 mg cumulative milk protein at week 18.

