Appendix 2. Injectable Epinephrine Training Form

Appendix 3. Serious Adverse Event Form (Sample)

Appendix 4. Protocol Deviation Form (Sample)

CLINICAL STUDY PROTOCOL SYNOPSIS

Title	A phase 2, multicenter, randomized, double-blind, placebo-controlled study to evaluate the efficacy and safety of dupilumab and milk oral immunotherapy for the treatment of patients with cow's milk allergy
Short Title	MAGIC Study
IND Number	██████████
Clinical Phase	Phase II
Site Locations	3 academic sites: Stanford University in California; Mayo Clinic and Phoenix Children's Hospital in Arizona
Study Objectives	
Primary objective
 
 • To assess whether dupilumab as an adjunct to milk oral immunotherapy (OIT) compared to placebo improves desensitization and safety, defined as an increase in the proportion of subjects who pass a double-blind placebo-controlled food challenge (DBPCFC) to at least 2040 mg cumulative milk protein at week 18 
Secondary objectives
 
 • Clinical 
 ◦ To assess the effect of dupilumab (compared to placebo) on ability to tolerate ≥1040 mg and 4040 mg cumulative milk protein at week 18 DBPCFCs ◦ To assess the effect of dupilumab (compared to placebo) on ability to tolerate ≥1040 mg, ≥2040 mg, and 4040 mg cumulative milk protein at week 24 DBPCFCs ◦ To compare levels of desensitization, defined as an increase in the cumulative tolerated protein dose (log transformed) of milk protein, from baseline to week 18 and baseline to week 24 DBPCFCs across treatment cohorts • Safety 
 ◦ To compare the rates and severity of OIT-induced gastrointestinal symptoms in subjects receiving dupilumab compared to placebo. ◦ To compare the safety of each treatment cohort as measured by rate and severity of allergic and non-allergic AEs during respective study phases ◦ To compare rates of study completion among treatment cohorts • Exploratory and Mechanistic 
 ◦ To explore the relationship between OIT-induced gastrointestinal symptoms and esophageal eosinophilia in subjects receiving dupilumab compared to placebo, if data is available ◦ To evaluate the immunological responses associated with OIT-induced AEs and successful desensitization

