--	---

Primary Endpoint	Proportion of subjects treated with dupilumab plus milk protein OIT vs placebo plus milk protein OIT who tolerate at least 2040 mg (cumulative) cow's milk protein during DBPCFC to milk at week 18
Secondary Endpoints	
Clinical
 
 Proportion of participants who tolerate at least 1040 mg cumulative milk protein at week 18 DBPCFC Proportion of participants who tolerate 4040 mg cumulative milk protein at week 18 DBPCFC Proportion of participants who tolerate at least 1040 mg cumulative milk protein at week 24 DBPCFC Proportion of participants who tolerate at least 2040 mg cumulative milk protein at week 24 DBPCFC Proportion of participants who tolerate 4040 mg cumulative milk protein at week 24 DBPCFC Change in the cumulative tolerated dose (CTD) of milk protein during DBPCFC from baseline to week 18 and baseline to week 24 across cohorts as pairwise comparisons of all treatment groups 
 Due to the positive skew for the distribution of the CTD, a log transformation will be applied to reduce the skewness 
Safety
 
 The rate and severity of OIT-induced gastrointestinal symptoms in subjects receiving dupilumab compared to placebo. Proportion of participants who have OIT-induced gastrointestinal symptoms, dupilumab compared to placebo The rate and severity of AEs, SAEs, and safety events in each cohort Proportion of participants completing the study among cohorts 
Exploratory and Mechanistic
 
 Change from baseline to week 24 in the log-transformed minimum concentration of milk protein which activates basophils, comparison between dupilumab and placebo Percent change from baseline to week 24 in milk-specific and total IgE and milk-specific and total IgG4, comparison between dupilumab and placebo Percent change from baseline to week 24 in milk SPT response, comparison between dupilumab and placebo Proportion of subjects experiencing esophageal eosinophilia, dupilumab compared to placebo, if data is available
Procedures and Assessments	The efficacy of dupilumab will be assessed by DBPCFC at week 18 (primary and secondary) and week 24 (secondary). Overall safety will be assessed by monitoring/evaluation of allergic reactions, treatment-emergent adverse events (TEAEs), physical examinations, and vital signs at pre-specified time points.

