2.3. Secondary Objectives

Clinical

- To assess the effect of dupilumab (compared to placebo) on tolerance of cumulative doses of ≥ 1040 mg and 4040 mg milk protein at week 18 DBPCFC
- To assess the effect of dupilumab (compared to placebo) on tolerance of cumulative doses of ≥ 1040 mg, ≥ 2040 mg, and 4040 mg milk protein at week 24 DBPCFC
- To compare levels of desensitization, defined as an increase in the cumulative tolerated protein dose (log transformed) of milk protein, from baseline to week 18 and baseline to week 24 DBPCFCs across treatment cohorts

Safety

- To compare the rates and severity of OIT-induced gastrointestinal symptoms in subjects receiving dupilumab compared to placebo.
- To compare the safety of each treatment cohort as measured by rate and severity of allergic and non-allergic AEs during respective study phases
- To compare rates of study completion among treatment cohorts

Exploratory and Mechanistic

[figure not shown]
- To explore the relationship between OIT-induced gastrointestinal symptoms and esophageal eosinophilia in subjects receiving dupilumab compared to placebo, if data is available
- To evaluate the immunological responses associated with OIT-induced AEs and successful desensitization

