3.5. Primary and Secondary Endpoints

3.5.1. Primary Endpoint

- Proportion of subjects treated with dupilumab plus milk protein OIT vs placebo plus milk protein OIT who tolerate at least 2040 mg (cumulative) cow's milk protein during DBPCFC to milk at week 18

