13.1. Statistical Hypothesis

The primary efficacy endpoint is the proportion of subjects who tolerate a cumulative dose of at least 2040 mg milk protein during a DBPCFC at week 18. The comparison between the dupilumab plus milk OIT arm (Cohort A) and the placebo plus milk OIT (Cohort B) arm will be made.

Letting p_D (and p_P) be the true proportion of subjects who tolerate a cumulative dose of at least 2040 mg milk protein during a DBPCFC at week 18 in the treatment arms of dupilumab + milk OIT and placebo + milk OIT, respectively. The following hypothesis for the superiority testing will be tested at the 5% 2-sided significance level:

$H_0: p_D = p_P$, i.e. the proportion of subjects who tolerate a cumulative dose of at least 2040 mg milk protein during a DBPCFC at week 18 is the same between dupilumab + OIT arm and the placebo + OIT arm

against the alternative

$H_a: p_D \neq p_P$, i.e. the proportion of subjects who tolerate a cumulative dose of at least 2040 mg milk protein during a DBPCFC at week 18 are different between the dupilumab + OIT arm and the placebo + OIT arm

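### The primary objective defines improved safety as passing the week-18 food challenge, so a positive primary result could be reported as meeting a safety objective that the endpoint does not measure

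*Combined protocol and SAP*

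**What the plan says.** The primary objective in Section 2.2 is to assess whether adjunct dupilumab "improves desensitization and safety, defined as an increase in the proportion of subjects who pass a double-blind placebo-controlled food challenge" to at least 2040 mg cumulative milk protein at week 18. The synopsis has the same wording under Study Objectives: "compared to placebo improves desensitization and safety, defined as an increase in the proportion of subjects who pass".

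The endpoint attached to this objective (Section 3.5.1) is the proportion in each arm "who tolerate at least 2040 mg (cumulative) cow's milk protein during DBPCFC to milk at week 18". It has no adverse event component. Section 13.1 names it as efficacy: "The primary efficacy endpoint is the proportion of subjects who tolerate a cumulative dose of at least 2040 mg milk protein". Section 13.5.1 analyses it under the title of primary efficacy analysis.

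Safety is handled elsewhere:

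- Section 1.2.1: "The differences in safety and tolerability will be assessed through an evaluation of treatment differences in AEs and study drop-out rates".
- Synopsis, Procedures and Assessments: "Overall safety will be assessed by monitoring/evaluation of allergic reactions, treatment-emergent adverse events (TEAEs), physical examinations, and vital signs". The preceding sentence there assigns the challenge to efficacy.
- Section 2.3, secondary safety objectives: "To compare the safety of each treatment cohort as measured by rate and severity of allergic and non-allergic AEs during respective study phases".
- Section 3.5.2 lists four safety endpoints: rate and severity of OIT-induced gastrointestinal symptoms, proportion of participants with them, rate and severity of adverse events, and proportion completing.
- Section 13.6.1 plans adverse event summaries by arm as numbers and percentages.

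**The concern.** The objective makes two claims and gives one measure for both. If the primary null is rejected in dupilumab's favour, the objective as written has been met in full, its safety half included, although the analysis contained no comparison of event rates or severity. A report could then present improved safety of OIT as a primary finding.

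Two features of the plan raise the stakes a little. First, Section 13.8 allows the trial to stop on the primary endpoint alone after 40 participants (20 per arm). A stop there would also meet the objective as worded. Section 13.7 then limits summaries after premature termination to what regulators require, so the between-arm safety comparison sought in Section 2.3 is not assured. Second, Section 11.2.1 records expected, related symptoms within two hours of dosing or a challenge as dosing reactions and not as adverse events. Exceptions are made for home-dosing episodes that are Grade 3 or higher or serious. Section 13.6.1 summarises adverse events and does not mention dosing reactions. Many up-dosing reactions could therefore be missing from the planned safety tables, and the primary safety wording might be relied on in their place.

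**Working it through.** The point is about wording, so the main check sets the sections side by side.

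**1. What the objective asserts.** Sections 2.2 and the synopsis: desensitization and safety, with one definition, passing the week-18 challenge.

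**2. What is tested.** Section 13.1: H0 is p_D = p_P, where p is the proportion tolerating at least 2040 mg cumulative at week 18. Rejecting H0 supports a statement about these two proportions and nothing else.

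**3. How the rest of the protocol divides the two ideas.** Section 2.1 gives desensitization and a lower rate and severity of adverse events as two separate effects. Section 1.2.1, the synopsis, Section 2.3 and Section 13.6.1 all place safety with events, reactions and drop-out. Only the primary objective merges them.

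**4. Whether passing implies few reactions.** Section 5.6 lets a dose be repeated or reduced after moderate or severe symptoms. Section 6.4 lets a participant be held at a dose or down-dosed. Section 3.1 then challenges all subjects at week 18 and sets no minimum daily dose. A participant with repeated reactions during up-dosing can be a responder. Risks of dupilumab itself, such as the conjunctivitis and helminthic infections among the events of special interest in Section 11.2.5, are not measured by a milk challenge.

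**5. What the sample size was built on.** Inputs from Section 13.2: 20% versus 55%, two-sided 5%, Fisher exact test, 44 per arm.

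- Exact enumeration gives power 0.908 at 44 per arm (0.904 at 43), so the stated 90% reproduces.
- Inflation for 25% drop-out: 44 / (1 − 0.25) = 58.7, against the stated 58 per arm.

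Both rates are challenge response rates. No event rate is assumed, so no power was planned for a safety conclusion.

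**6. Illustration of what a direct safety comparison could show.** Assume 40% with gastrointestinal symptoms on placebo (the figure Section 1.1 gives for milk OIT) and 58 per arm. The dupilumab rates are my assumption. Power is the two-sided 5% normal approximation without continuity correction. The half-width is 1.96 × √[(p1(1−p1) + p2(1−p2)) / 58].

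| Dupilumab rate | Power | 95% CI half-width for the difference |
|---|---|---|
| 15% | 0.86 | 1.96 × √(0.3675/58) = 0.156 |
| 20% | 0.66 | 1.96 × √(0.4000/58) = 0.163 |
| 25% | 0.41 | 1.96 × √(0.4275/58) = 0.168 |

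On these assumptions a halving of gastrointestinal symptoms would be detected about two times in three, and the difference would be known to within about 16 points either way. That suits estimation better than a confirmatory claim.

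**The case against.** The strongest reply is that every operative part of the plan is already clear. The endpoint, the hypotheses and the primary analysis concern efficacy only, and no rule in the plan turns a rejected null into a safety conclusion. This stands. A reader might infer that a positive result would be taken as a safety finding, or that the test itself is compromised. The documents support neither. They support only that the result could be reported that way.

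A second reply is that the definition may belong to desensitization alone, since Section 2.3 uses the same construction for desensitization without mentioning safety. That reading is possible. It leaves safety as a primary objective with no definition and no primary endpoint, so the same edit is needed.

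A third reply is that the endpoint does carry tolerability information. A reader might infer that no safety event enters the primary test, and that is too strong:

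- Challenges are stopped by graded reactions (Section 3.1).
- Withdrawals and missing results count as non-response (Section 13.5.1), and Section 10.1 lists serious adverse events and anaphylaxis with hypotension among the reasons for termination.
- Participants who do not tolerate 5 mg at Visit 4 are treatment failures and receive no further treatment (Section 3.4).
- Table 1 takes a participant from 20 mg to 1000 mg in six steps, and there are six up-dosing visits from Visit 5 to Visit 10. Each repeated dose therefore leaves the participant at least one step lower at the challenge.

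These routes are real but indirect. They do not count or grade events during OIT, and a participant who stops study drug may stay in the study for later visits (Section 6.5.2).

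Finally, it is tempting to fault the plan because Section 13.5.4 leaves the safety endpoints outside the testing hierarchy. That is not a defect. The plan promises no confirmatory safety inference.

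**Conclusion.** The concern holds as a fault of wording and interpretation. The primary objective, in two places, attaches a safety claim to a measure that the rest of the protocol calls efficacy and that reflects tolerability only indirectly. A positive primary test at the interim or final analysis could be presented as meeting a safety objective.

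Its weight is small. The hypothesis test, the sample size of 44 evaluable and 58 enrolled per arm, alpha and power are all unaffected. The conclusion rests on the literal text of the objective. The alternative reading leads to the same correction. It does not rest on the illustrative event rates above, which show only the precision a direct comparison might have.

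**What to change.** 1. Delete the words *and safety* from the primary objective in Section 2.2 and in the synopsis.
2. State in Section 13.6 that safety conclusions rest on the existing secondary safety endpoints in Section 3.5.2, reported as between-arm estimates with 95% confidence intervals and without a confirmatory claim. The planned counts and percentages do not by themselves give the comparison that Section 2.3 asks for.
3. Include in these analyses the events that Section 11.2.1 records as dosing reactions, so that up-dosing reactions are counted. An analysis of recorded adverse events alone could miss many of them.

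The sponsor gives up the primary safety wording and does slightly more descriptive analysis. No procedure, sample size, alpha or power changes.
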